7.3.2 Evaluating Adverse Events

An investigator who is a qualified physician will evaluate all adverse events according to the NCI Common Terminology for Adverse Events (CTCAE), version 5.0. Any adverse event which changes CTCAE grade over the course of a given episode will have each change of grade recorded on the adverse event case report forms/worksheets.

If CTCAE grading does not exist for an adverse event, the severity of mild, moderate, severe, and life-threatening, corresponding to Grades 1-4, will be used. Subjects will be monitored by medical histories, physical examinations, and blood studies to detect potential toxicities from the treatment.

Table 6 Evaluating Adverse Events

An investigator who is a qualified physician, will evaluate all adverse events as to:

V5.0 CTCAE Grading	Grade 1	Mild; asymptomatic or mild symptoms; clinical or diagnostic observations only; intervention not indicated.
	Grade 2	Moderate; minimal, local or noninvasive intervention indicated; limiting age-appropriate instrumental ADL.
	Grade 3	Severe or medically significant but not immediately life-threatening; hospitalization or prolongation of hospitalization indicated; limiting self-care ADL.
	Grade 4	Life threatening consequences; urgent intervention indicated.
	Grade 5	Death related to AE
Seriousness	A serious adverse event is any adverse event occurring at any dose or during any use of pembrolizumab that:	
	† Results in death ; or	
	† Is life threatening ; or places the subject, in the view of the investigator, at immediate risk of death from the event as it occurred (Note: This does not include an adverse event that, had it occurred in a more severe form, might have caused death.); or	
	† Results in a persistent or significant disability/incapacity (substantial disruption of one's ability to conduct normal life functions); or	
	† Results in or prolongs an existing inpatient hospitalization (hospitalization is defined as an inpatient admission, regardless of length of stay, even if the hospitalization is a precautionary measure for continued observation. (Note: Hospitalization [including hospitalization for an elective procedure] for a preexisting condition which has not worsened does not constitute a serious adverse event.); or	
	† Is a congenital anomaly/birth defect (in offspring of subject taking the product regardless of time to diagnosis); or	

This document is confidential and the property of the University of Pennsylvania. No part of it may be transmitted, reproduced, published, or used by other persons without prior written authorization from the regulatory sponsor.

	
Is a new cancer; (that is not a condition of the study) or
 
Is an overdose (whether accidental or intentional). Any adverse event associated with an overdose is considered a serious adverse event. An overdose that is not associated with an adverse event is considered a non-serious event of clinical interest and must be reported within 24 hours.
 
Other important medical events that may not result in death, not be life threatening, or not require hospitalization may be considered a serious adverse event when, based upon appropriate medical judgment, the event may jeopardize the subject and may require medical or surgical intervention to prevent one of the outcomes listed previously (designated above by a †).
						
Duration	Record the start and stop dates of the adverse event. If less than 1 day, indicate the appropriate length of time and units						
Action taken	Did the adverse event cause pembrolizumab to be discontinued?						
Relationship to test drug	
Did pembrolizumab cause the adverse event? The determination of the likelihood that pembrolizumab caused the adverse event will be provided by an investigator who is a qualified physician. The investigator’s signed/dated initials on the source document or worksheet that supports the causality noted on the AE form, ensures that a medically qualified assessment of causality was done. This initialed document must be retained for the required regulatory time frame. The criteria below are intended as reference guidelines to assist the investigator in assessing the likelihood of a relationship between the test drug and the adverse event based upon the available information.
 
The following components are to be used to assess the relationship between pembrolizumab and the AE; the greater the correlation with the components and their respective elements (in number and/or intensity), the more likely pembrolizumab caused the adverse event (AE):
 
 
 Exposure	Is there evidence that the subject was actually exposed to pembrolizumab such as: reliable history, acceptable compliance assessment (pill count, diary, etc.), expected pharmacologic effect, or measurement of drug/metabolite in bodily specimen?	
 
 Time Course	Did the AE follow in a reasonable temporal sequence from administration of pembrolizumab? Is the time of onset of the AE compatible with a drug-induced effect (applies to trials with investigational medicinal product)?	
 
 Likely Cause	Is the AE not reasonably explained by another etiology such as underlying disease, other drug(s)/vaccine(s), or other host or environmental factors	
 
	Exposure	Is there evidence that the subject was actually exposed to pembrolizumab such as: reliable history, acceptable compliance assessment (pill count, diary, etc.), expected pharmacologic effect, or measurement of drug/metabolite in bodily specimen?	Time Course	Did the AE follow in a reasonable temporal sequence from administration of pembrolizumab? Is the time of onset of the AE compatible with a drug-induced effect (applies to trials with investigational medicinal product)?	Likely Cause	Is the AE not reasonably explained by another etiology such as underlying disease, other drug(s)/vaccine(s), or other host or environmental factors
Exposure	Is there evidence that the subject was actually exposed to pembrolizumab such as: reliable history, acceptable compliance assessment (pill count, diary, etc.), expected pharmacologic effect, or measurement of drug/metabolite in bodily specimen?						
Time Course	Did the AE follow in a reasonable temporal sequence from administration of pembrolizumab? Is the time of onset of the AE compatible with a drug-induced effect (applies to trials with investigational medicinal product)?						
Likely Cause	Is the AE not reasonably explained by another etiology such as underlying disease, other drug(s)/vaccine(s), or other host or environmental factors						

Relationship to Pembrolizumab (continued)	The following components are to be used to assess the relationship between the test drug and the AE: (continued)	
	Dechallenge	
Was pembrolizumab discontinued or dose/exposure/frequency reduced? If yes, did the AE resolve or improve? If yes, this is a positive dechallenge. If no, this is a negative dechallenge. (Note: This criterion is not applicable if: (1) the AE resulted in death or permanent disability; (2) the AE resolved/improved despite continuation of pembrolizumab; or (3) the trial is a single-dose drug trial); or (4) pembrolizumab is/are only used one time.)

	Rechallenge	
Was the subject re-exposed to pembrolizumab in this study? If yes, did the AE recur or worsen? If yes, this is a positive rechallenge. If no, this is a negative rechallenge. (Note: This criterion is not applicable if: (1) the initial AE resulted in death or permanent disability, or (2) the trial is a single-dose drug trial); or (3) pembrolizumab is used only one time.)

This document is confidential and the property of the University of Pennsylvania. No part of it may be transmitted, reproduced, published, or used by other persons without prior written authorization from the regulatory sponsor.

		NOTE: IF A RECHALLENGE IS PLANNED FOR AN ADVERSE EVENT WHICH WAS SERIOUS AND WHICH MAY HAVE BEEN CAUSED BY PEMBROLIZUMAB, OR IF REEXPOSURE TO PEMBROLIZUMAB POSES ADDITIONAL POTENTIAL SIGNIFICANT RISK TO THE SUBJECT, THEN THE RECHALLENGE MUST BE APPROVED IN ADVANCE BY THE U.S. CLINICAL MONITOR AS PER DOSE MODIFICATION GUIDELINES IN THE PROTOCOL.
	Consistency with Trial Treatment Profile	Is the clinical/pathological presentation of the AE consistent with previous knowledge regarding pembrolizumab or drug class pharmacology or toxicology?
The assessment of relationship will be reported on the case report forms /worksheets by an investigator who is a qualified physician according to his/her best clinical judgment, including consideration of the above elements.		
Record one of the following	Use the following scale of criteria as guidance (not all criteria must be present to be indicative of a pembrolizumab relationship).	
Yes, there is a reasonable possibility of pembrolizumab relationship.	There is evidence of exposure to pembrolizumab. The temporal sequence of the AE onset relative to the administration of pembrolizumab is reasonable. The AE is more likely explained by pembrolizumab than by another cause.	
No, there is not a reasonable possibility pembrolizumab relationship	Subject did not receive pembrolizumab OR temporal sequence of the AE onset relative to administration of pembrolizumab is not reasonable OR there is another obvious cause of the AE. (Also entered for a subject with overdose without an associated AE.)	

This document is confidential and the property of the University of Pennsylvania. No part of it may be transmitted, reproduced, published, or used by other persons without prior written authorization from the regulatory sponsor.

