2.0 TRIAL DESIGN

2.1 Trial Design

This is a single center, open label trial of pembrolizumab in patients failing to respond to or relapsing after anti-CD19 chimeric antigen receptor modified T cell therapy (CTL019/CTL119) for relapsed or refractory CD19+ lymphomas.

Eligible patients will have CD19+ diffuse large B-cell, follicular, or mantle cell lymphomas with no available curative treatment options, a limited prognosis of several months to <2 years anticipated survival with currently available therapies, and progressive or relapsed disease after a single intravenous dose of $5 \times 10^8 \pm 20\%$ CTL019/CTL119 administered on our currently enrolling clinical trial (NCT02030834). We anticipate enrollment of 12 total patients onto the present trial for patients not responding to, or relapsing after, CTL019/CTL119.

[figure not shown]
The safety and efficacy of pembrolizumab in this group of patients will be determined using a fixed dose of 200mg IV. This dose was previously well-tolerated and effective for treatment of patients with metastatic melanoma and NSCLC. The primary safety endpoint will be determined by assessing the rate of pembrolizumab discontinuation as well as the rate of occurrence of treatment-related adverse events (AEs), defined as NCI CTCAE version 5 grade ≥ 3 AEs are possibly, probably, or definitely related to study treatment or grade 4 cytokine release syndrome. Secondary efficacy endpoints will be assessed, including overall response rate (ORR) and progression-free survival (PFS).

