4.2.3 Rationale for Endpoints

4.2.3.1 Rationale for Efficacy Endpoints

- 1) **Primary Objective:** To determine the safety of pembrolizumab in patients failing to respond to or relapsing after anti-CD19 chimeric antigen receptor modified T cell therapy for relapsed or refractory CD19+ lymphomas.

Although pembrolizumab has been approved for use in melanoma, there have been no studies in non-Hodgkin lymphoma and the transition to a fixed dose has not been well-studied. In previous studies of pembrolizumab, the rates of drug discontinuation due to an adverse event were 4.2% in melanoma and 2.6% in non-small cell lung cancer and the rates of drug discontinuation for any reason were 9.4% in melanoma and 21.1% in non-small cell lung cancer (see Investigator's Brochure). Additionally, given that we hypothesize that pembrolizumab may re-activate quiescent chimeric antigen receptor T cells, there is the potential for additional toxicity in patients who have previously received chimeric antigen receptor T cells. Thus, we will define safety as ≤ 30% of patients experiencing toxicities resulting in discontinuation of pembrolizumab.

This document is confidential and the property of the University of Pennsylvania. No part of it may be transmitted, reproduced, published, or used by other persons without prior written authorization from the regulatory sponsor.

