8.0 STATISTICAL ANALYSIS PLAN

8.1 Statistical Analysis Plan

8.1.1 Primary Objectives & Hypotheses

(1) Objective: To determine the safety of pembrolizumab in patients failing to respond to or relapsing after anti-CD19 chimeric antigen receptor modified T cell therapy for relapsed or refractory CD19+ lymphomas. Safety will be assessed by adverse event monitoring. Patients who have received at least one dose of pembrolizumab will be considered evaluable for safety. In this trial, success will be defined as receiving at least one dose of pembrolizumab and the lack at least possibly related adverse events leading to permanent discontinuation of pembrolizumab. Patients who experience Grade 3 or higher non-hematologic toxicity leading to permanent pembrolizumab discontinuation or any Grade 4 non-hematologic toxicity or cytokine release syndrome at least possibly related to pembrolizumab will be considered toxicity failures.

Methodology: We will use a Bayesian monitoring rule to assure that the failure rate is no greater than 30%. Monitoring will begin with the first patient. Because little information is available on the safety of this drug in lymphoma, we will assume a non-informative Beta(1, 1) prior distribution for the failure rate. We will denote the rate of pembrolizumab discontinuation as failure rate, FR, and will use the following monitoring rule in the interest of patient safety: we will stop the trial if at any time: $\Pr[\text{FR} > 0.30 \mid \text{data from the trial}] \geq 97.5\%$

That is, if at any time during the study, we can conclude that there is at least a 97.5% chance that the failure rate is greater than 30%, we will stop the study. The stopping boundaries corresponding to this probability criterion are to terminate the trial if:

$(\# \text{ of patients that experience failure}) / (\# \text{ of patients evaluated}) \geq 3/3, 3/4, 4/5, 4/6, 5/7, 5/8, 6/9, 6/10, 7/11, 7/12$. Any patient who has received at least one dose of pembrolizumab will be included in this denominator for evaluable patients if they have received at least 4 doses of pembrolizumab and not experienced toxicity OR if they have experienced any toxicity with any dose of pembrolizumab.

If the study is not terminated early, it will continue until all patients have been treated with pembrolizumab and completed all follow up evaluations.

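### The safety endpoint counts events at least possibly related to pembrolizumab, but the adverse event form's Yes box carries a stricter criterion and is never mapped to that threshold, so failures may be under-counted

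*Combined protocol and SAP*

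**What the plan says.** **Endpoint.** Section 8.1.1 defines success by "the lack at least possibly related adverse events leading to permanent discontinuation of pembrolizumab". In the failure definition, "any Grade 4 non-hematologic toxicity or cytokine release syndrome at least possibly related to pembrolizumab will be considered toxicity failures", alongside Grade 3 or higher non-hematologic toxicity that leads to permanent discontinuation. The threshold is a single cut at possible.

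**Design section.** Section 2.1 describes the relevant adverse events as those "possibly, probably, or definitely related to study treatment or grade 4 cytokine release syndrome", which is a three-level scale of relatedness.

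**Form.** Table 6 in section 7.3.2 has the investigator record one of two answers. Yes is labelled as a reasonable possibility of a relationship. Three guidance points stand beside it: exposure, reasonable timing, and "The AE is more likely explained by pembrolizumab than by another cause". No is guided by absence of exposure, unreasonable timing, or that "there is another obvious cause of the AE". The table adds that the criteria are guidance, that not all need be met, and that the investigator's best judgment decides.

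**Mapping.** No section says how Yes or No translates into the threshold in section 8.1.1, and no field that separates possible from probable is described.

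**The concern.** The third guidance point under Yes asks whether pembrolizumab is the more likely explanation. That is a probable-level test, while the endpoint needs only a possible relationship. The likely-cause element earlier in Table 6 leans the same way, because it asks whether the event lacks a reasonable explanation in underlying disease, other drugs or other factors.

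Rival explanations will be common here. Every patient has relapsed or refractory lymphoma and has had CTL019/CTL119. The label and the criterion beside it set different thresholds, so two careful investigators could code the same event differently. The criterion is stricter than the endpoint and never looser, so a bias from this source would reduce the failure count. That count decides both the primary safety conclusion and whether the trial stops.

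**Working it through.** **1. The passages side by side**

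| Place | Threshold or scale |
|---|---|
| 8.1.1, success and failure definitions | at least possibly related (one cut) |
| 2.1 | possibly / probably / definitely |
| Table 6, label of Yes | reasonable possibility |
| Table 6, third criterion under Yes | more likely pembrolizumab than another cause |
| Table 6, No | no exposure, unreasonable timing, or another obvious cause |

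Take an event with exposure, reasonable timing and a plausible but not obvious rival cause, judged no more likely due to pembrolizumab than to that cause. It meets the endpoint's threshold. On the form it meets the label of Yes and two of its three criteria, fails the third, and meets none of the criteria for No. The form does not settle the answer.

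**2. The plan's own figures**

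The only stated figures that this attribution feeds are the stopping boundaries. Inputs from section 8.1.1 are a Beta(1,1) prior and a stop if Pr[FR > 0.30 | data] ≥ 0.975. With x failures in n patients, the posterior is Beta(1 + x, 1 + n − x).

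- Seven of the ten listed boundaries reproduce as the smallest qualifying count: 3/3 (0.992), 4/5 (0.989), 5/7 (0.989), 6/9 (0.989), 6/10 (0.978), 7/11 (0.991), 7/12 (0.982).
- Three fall just short of 0.975: 3/4 (0.969), 4/6 (0.971), 5/8 (0.9747). The exact rule gives 4/4, 5/6 and 6/8.

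That discrepancy is separate from this point. The listed boundaries are used below, with the exact rule beside them.

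**3. What one event can change**

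If one failure is recoded as a non-failure and the patient stays in the denominator, the posterior at the listed boundaries drops to between 0.837 and 0.961, so the trial does not stop. For example, 7/12 gives 0.982 and 6/12 gives 0.938. For the final criterion of at most 30%, 3/12 = 25% meets it and 4/12 = 33% does not.

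**4. Illustration with assumed miss shares**

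Let p be the true failure rate and m the share of true failures coded No. The recorded rate is p(1 − m). P(stop) is an exact binomial enumeration with a check after each patient. P(≤3 of 12) is the binomial probability at n = 12, ignoring early stopping. For p = 0.40:

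| m (assumed) | Recorded rate | P(stop), listed | P(stop), exact rule | P(≤3 of 12) |
|---|---|---|---|---|
| 0 | 0.40 | 0.313 | 0.242 | 0.225 |
| 0.10 | 0.40 × 0.90 = 0.36 | 0.232 | 0.167 | 0.320 |
| 0.25 | 0.40 × 0.75 = 0.30 | 0.134 | 0.085 | 0.493 |
| 0.50 | 0.40 × 0.50 = 0.20 | 0.038 | 0.018 | 0.795 |

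At p = 0.50, P(stop) with the listed boundaries is 0.550, 0.428, 0.261 and 0.076 for the same values of m. At p = 0.30, m of 0, 0.10 and 0.50 gives 0.134, 0.097 and 0.015.

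**The case against.** A reader might infer that possible events are bound to drop out of the failure count. The documents do not support that. The Yes box is itself labelled a reasonable possibility, its criteria are guidance that need not all be met, and No requires an obvious other cause, which is narrower than any rival cause. A possible event can properly be recorded as Yes. Because section 8.1.1 uses a single cut, a two-box form can also serve it.

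A reader might also infer that investigators would record the CAR T cells as the obvious other cause. The protocol's own rationale points the other way. Section 4.2.3.1 says "pembrolizumab may re-activate quiescent chimeric antigen receptor T cells" and treats this as a source of added toxicity. Section 5.4.2 anticipates cytokine release syndrome after pembrolizumab in these patients, and section 5.2.1.2 classes grade 4 cytokine release syndrome as drug toxicity. What is missing is one sentence in the attribution guidance that says so.

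There are safeguards. Section 7.3.1.1 presumes an event of clinical interest to be immune-related if no other cause is found. Section 10.4 has an independent medical monitor review toxicity assignments. Section 7.3 explains reasonable possibility, for IRB reporting, as evidence suggesting causation. They help only in part: the presumption does not apply when a rival cause exists, the monitor is given no different threshold, and the IRB definition is not tied to the form.

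Finally, section 8.1.1 also calls the failure rate the rate of pembrolizumab discontinuation, and an investigator who stops the drug for an immune-related event has normally already judged it related. This limits the exposure for many events but does not remove the mismatch. It is also a fair objection that the miss shares have no basis in the documents.

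**Conclusion.** The mismatch stands. The endpoint uses a possible threshold, the form's Yes guidance contains a probable-level criterion, and nothing links the two. Possibly but not probably related events may be coded No, inconsistently between assessors, and the bias would run toward too few failures.

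How often this would happen cannot be derived from the documents. The tabulated probabilities show sensitivity and do not predict a rate. They assume a uniform miss share, independent patients, and miscoded patients who stay in the denominator as non-failures. What needs no assumed miss share is that, with 12 patients, a single reclassified event can decide whether the 30% criterion is met. This should be corrected because it feeds the primary safety endpoint and the stopping rule, and because correction is cheap.

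**What to change.** 1. In Table 6 and section 8.1.1, state that Yes means at least possibly related to pembrolizumab, including events that arise through re-activation of CAR T cells, consistent with sections 4.2.3.1 and 5.4.2.
2. Replace the more-likely criterion under Yes with wording at the possible threshold.
3. State in section 8.1.1 that every Yes event meeting that section's other conditions counts as a failure, and use the same term in section 2.1.
4. Re-check No attributions already recorded for events that led to discontinuation, Grade 4 non-hematologic events and cytokine release syndrome.

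The cost is one table, one form and a short review of records in about a dozen patients. No dosing or treatment rule changes. The downside is that the recorded failure rate may rise slightly. A graded attribution scale, counting possible or higher, is an optional alternative and is not required. A test that pembrolizumab cannot be ruled out would arguably be broader than possible and would change the endpoint instead of aligning the form with it.

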7.3.3 Modification of CTC Grading scale for Cytokine Release Syndrome (CRS)

The CTCAE grading system was developed to capture a cytokine release syndrome occurring during infusional therapy and is inadequate to capture the delayed CRS that occurs after CART-19 infusions. We propose to modify the CTC grading specifically to capture toxicity for protocols using CART-19 cells (Table 7.2.5a). Related definitions can be found in **Table 7.2.5b**.

Recipients of CART-19 cells may develop a cytokine release syndrome. Data from small numbers of patients show marked elevations in IL6, IFN-g, and less intensely TNF among other cytokines. Elevations in clinically available markers of inflammation including ferritin and CRP have also been observed to correlate with the clinical CRS syndrome.

Symptoms usually occur 1-14 days after cell infusion, but the syndrome is not defined by the timing of the reaction. Patients developing any symptoms attributable by the investigator as related to cytokine release should be reported as having had a CRS. Symptoms may include:

- High fevers
- Rigors
- Sweating
- Nausea
- Vomiting
- Anorexia
- Fatigue
- Headache
- Myalgia/arthralgia
- Hypotension
- Dyspnea
- Tachypnea
- Hypoxia
- Altered mental status
- End organ dysfunction
- Signs of macrophage activation syndrome including hemophagocytosis and hemolysis

For the purposes of reporting and grading on clinical trials using CART-19 cells, we will use the following grading for CRS Toxicity. The start date of CRS is a retrospective assessment of the date of onset of persistent fevers and/or myalgia consistent with CRS and not explained by other events (i.e. sepsis). The stop date of CRS is defined as the date when the patient has been afebrile for 24 hours and off vasopressors for 24 hours.

This document is confidential and the property of the University of Pennsylvania. No part of it may be transmitted, reproduced, published, or used by other persons without prior written authorization from the regulatory sponsor.

Table 7.2.5a - CRS Toxicity Grading				
1	2	3	4	5
Mild reaction: Treated with supportive care such as anti-pyretics, anti-emetics	Moderate reaction requiring IV fluids or parenteral nutrition; some signs of organ dysfunction (i.e. grade 2 creatinine or grade 3 liver function tests ([LFTs] related to CRS and not attributable to any other condition). Hospitalization for management of CRS related symptoms including fevers with associated neutropenia.	More severe reaction: Hospitalization required for management of symptoms related to organ dysfunction including: 
 • grade 4 LFTs • grade 3 creatinine related to CRS and not attributable to any other conditions • hypotension requiring multiple fluid boluses for blood pressure support or low-dose pressors (see Table 7.2.5b) • coagulopathy requiring fresh frozen plasma or cryoprecipitate • hypoxia requiring supplemental oxygen (nasal cannula oxygen, high flow oxygen, Continuous Positive Airway Pressure [CPAP] or Bilateral Positive Airway Pressure [BiPAP]) Patients admitted for management of suspected infection due to fevers and/or neutropenia may have grade 2	Life-threatening complications such as hypotension requiring high-dose pressors (see Table 7.2.5b) or hypoxia requiring mechanical ventilation	Death

This document is confidential and the property of the University of Pennsylvania. No part of it may be transmitted, reproduced, published, or used by other persons without prior written authorization from the regulatory sponsor.

Table 7.2.5a - CRS Toxicity Grading				
		CRS and this excludes management of fever or myalgias		

Table 7.2.5b High Dose Vasopressor Use

Definition of “High-Dose” Vasopressors	
Vasopressor	Dose for ≥ 3 hours
Norepinephrine monotherapy	≥ 20 mcg/kg/min
Dopamine monotherapy	≥ 10 mcg/kg/min
Phenylephrine monotherapy	≥ 200 mcg/min
Epinephrine monotherapy	≥ 10 mcg/min
If on vasopressin	High-dose if vaso + Norepinephrine Equivalent (NE) of >10 mcg/min (using Vasopressin and Septic Shock Trial (VASST) formula)
If on combination vasopressors (not vasopressin)	Norepinephrine equivalent of ≥ 20 mcg/min (using VASST formula)

Vasopressin and Septic Shock Trial (VASST) Equivalent Equation:

$$\text{Norepinephrine equivalent dose} = [\text{norepinephrine (mcg/min)}] + [\text{dopamine (mcg/kg/min)} \div 2] + [\text{epinephrine (mcg/min)}] + [\text{phenylephrine (mcg/min)} \div 10]$$

